6.2.5 Critical Structures

6.2.5.1 Critical Organ Dose-Volume Limits

The following table lists maximum dose limits to a point or volume within several critical organs. These are absolute limits, and treatment delivery that exceeds these limits will constitute a major protocol violation.

The limits for 20Gy x 3 are taken from RTOG 0236 and were formulated with the approval of the RTOG study committee (Principal Investigators and Co-Chairs) including [name], international authority on radiobiology and radiotolerance, using known tolerance data, radiobiological conversion models, norms used in current practice at academic centers,¹⁶⁻²² and the experience of several years of irradiation using these large fractions at Indiana University^{26,30,31} and centers in Sweden,^{24,25,27} Germany, and Japan. With the exception of the spinal cord limit which is conservatively set from experience with irradiation of vertebral body metastases, the dose limits for 30 Gy were scaled from the limits at 20 Gy per fraction. However, even for the 30 Gy arm, we will endeavor to meet the single fraction dose limits of the 20 Gy arm.

In order to verify each of these limits, the organs must be contoured such that appropriate dose volume histograms can be generated. Instruction for the contouring of these organs will follow below.

TABLE 2a: DOSE LIMITS TO CRITICAL STRUCTURES for 20 Gy x3

Organ		20 Gy x 3 Arm
	Volume	
Spinal Cord	Any point	18 Gy (6 Gy
		per fraction)
Esophagus	Any point	27 Gy (9 Gy
		per fraction)
Ipsilateral	Any point	24 Gy (8 Gy
Brachial Plexus		per fraction)
Heart	Any point	30 Gy (10 Gy
		per fraction)
Trachea and	Any point	30 Gy (10 Gy
Ipsilateral		per fraction)
Bronchus		
Whole Lung	(See table in	(See table
(Right & Left)	Section 6.4.2)	below)

TABLE 2b: DOSE LIMITS TO CRITICAL STRUCTURES for 30 Gy x1

Serial Tissue		Volume Max	Max Point Dose	Endpoint (≥Grade
	Volume	(Gy)	(Gy)	3)
Spinal Cord	<0.35 cc	10 Gy	14 Gy	myelitis
	<1.2 cc	7 Gy		
Esophagus*	<5 cc	11.9 Gy	15.4 Gy	stenosis/fistula
Brachial Plexus	<3 cc	14 Gy	17.5 Gy	neuropathy
Heart/Pericardi	<15 cc	16 Gy	22 Gy	pericarditis
um				
Great vessels	<10 cc	31 Gy	37 Gy	aneurysm
Trachea and	<4 cc	10.5 Gy	20.2 Gy	stenosis/fistula
Large				
Bronchus*				
Rib	<1 cc	22 Gy	30 Gy	Pain or fracture
Skin	<10 cc	23 Gy	26 Gy	ulceration
Stomach	<10 cc	11.2 Gy	12.4 Gy	ulceration/fistula
Parallel Tissue		Critical Volume		Endpoint (≥Grade
	Critical	Dose Max (Gy)		3)
	Volume			
	(cc)			
Lung (Right &	1500 cc	7 Gy		Basic Lung
Left)				Function
Lung (Right &	1000 cc	7.4 Gy		Pneumonitis
Left)				

6.2.5.2 Contouring of Normal Tissue Structures

6.2.5.2.1 Spinal Cord

The spinal cord will be contoured based on the bony limits of the spinal canal. The spinal cord should be contoured starting at least 10 cm above the superior extent of the PTV and continuing on every CT slice to at least 10 below the inferior extent of the PTV.

6.2.5.2.2 Esophagus

The esophagus will be contoured using mediastinal windowing on CT to correspond to the mucosal, submucosa, and all muscular layers out to the fatty adventitia. The esophagus should be contoured starting at least 10 cm above the superior extent of the PTV and continuing on every CT slice to at least 10 below the inferior extent of the PTV.

6.2.5.2.3 Brachial Plexus

The defined ipsilateral brachial plexus originates from the spinal nerves exiting the neuroforamina on the involved side from around C5 to T2. However, for the purposes of this protocol only the major trunks of the brachial plexus will be contoured using the subclavian and axillary vessels as a surrogate for identifying the location of the brachial plexus. This neurovascular complex will be contoured starting proximally at the bifurcation of the brachiocephalic trunk into the jugular/subclavian veins (or carotid/subclavian arteries) and following along the route of the subclavian vein to the axillary vein ending after the neurovascular structures cross the 2nd rib.

6.2.5.2.4 Heart

The heart will be contoured along with the pericardial sac. The superior aspect (or base) for purposes of contouring will begin at the level of the inferior aspect of the aortic arch (aorto-pulmonary window) and extend inferiorly to the apex of the heart.

6.2.5.2.5 Trachea and Proximal Bronchial Tree

The trachea and proximal bronchial tree will be contoured as two separate structures using mediastinal windows on CT to correspond to the mucosal, submucosa and cartilage rings and airway channels associated with these structures. For this purpose, the trachea will be divided into two sections: the proximal trachea and the distal 2 cm of trachea. The proximal trachea will be contoured as one structure, and the distal 2 cm of trachea will be included in the structure identified as proximal

bronchial tree. Differentiating these structures in this fashion will facilitate the eligibility requirement for excluding patients with tumors within 2 cm of the proximal bronchial tree (see section 6.5.2.8 below).

6.2.5.2.5.1 Proximal Trachea

Contouring of the proximal trachea should begin at least 10 cm superior to the extent of the PTV or 5 cm superior to the carina (which ever is more superior) and continue inferiorly to the superior aspect of the proximal bronchial tree (see definitions below).

6.2.5.2.5.2 Proximal Bronchial Tree

The proximal bronchial tree will include the most inferior 2 cm of distal trachea and the proximal airways. The following airways will be included according to standard anatomical relationships: the distal 2 cm of trachea, the carina, the right and left mainstem bronchi, the right and left upper lobe bronchi, the intermedius bronchus, the right middle lobe bronchus, the lingular bronchus, and the right and left lower lobe bronchi. Contouring of the lobar bronchi will end immediately at the site of a segmental bifurcation.

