3.2 Exclusion Criteria

- Prior Thoracic Radiation Therapy
- T2 or T3 tumor greater than 5 cm or T3 tumor based on chest wall involvement
- Node positive or metastatic disease
- Tumor location within the zone of the proximal bronchial tree. The proximal bronchial tree is defined as the carina, right and left main bronchi, right and left upper lobe bronchi, bronchus intermedius, right middle lobe bronchus, lingular bronchus, and right and left lower lobe bronchi. The *zone* of the proximal bronchial tree is defined as a volume 2cm in all directions around the proximal bronchial tree.
- Other conditions deemed by the PI or associates to make the patient ineligible for protocol investigations, procedures, and high-dose external beam radiotherapy. This includes the inability to cooperate with any aspect of SBRT such as the inability to lie still and breathe reproducibly.
- Pregnant or unwilling to use adequate contraception.

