4.2 Pre-treatment Data Acquisition

- PFT's (Full spirometry and DLCO)
- Urine pregnancy test for women of child bearing potential
- PET-CT
- CT of the Chest/Abdomen/Pelvis (CT Simulation is acceptable. The abdomen and pelvis CT studies may be omitted if the PET-CT covers the abdomen and pelvis.)
- Tumor Biopsy
- Specimens for banking: blood and urine (will be requested but is optional)
- Toxicity evaluation
- Quality of Life Questionnaire

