6.2.5.2.8 Proximal Bronchial Tree Plus 2 cm

As part of adhering to the ineligibility requirements for not enrolling patients with tumors in the zone of the proximal bronchial tree, it is convenient to define an artificial structure 2 cm larger in all directions from the proximal bronchial tree. If the GTV falls within this artificial structure, the patient should not be treated with the protocol therapy. Most treatment

planning systems have automatic contouring features that will generate this structure without prohibitive effort at the time of treatment planning. This structure is not required by the protocol, but its construction is suggested to facilitate appropriateness of patient selection. Alternately, ruler tools in the treatment planning software may be used to ensure protocol compliance.

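### The proximal bronchial tree is defined without the distal trachea for eligibility (3.2) but with it for contouring, so a tumor can pass 3.2 yet be barred from protocol treatment

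*Combined protocol and SAP*

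**What the plan says.** Three parts of the protocol bear on this.

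- **Section 3.2 (Exclusion Criteria)** excludes a tumor lying in a 2 cm zone around the proximal bronchial tree, and it defines the tree by a list: "The proximal bronchial tree is defined as the carina, right and left main bronchi, right and left upper lobe bronchi, bronchus intermedius", followed by the middle lobe, lingular and lower lobe bronchi. The trachea does not appear.
- **Section 6.2.5.2.5 (Trachea and Proximal Bronchial Tree)** splits the trachea for contouring and assigns its lowest part to the tree. Under 6.2.5.2.5.2: "The proximal bronchial tree will include the most inferior 2 cm of distal trachea and the proximal airways". The remaining airways match those in 3.2. The parent section gives the reason for the split: "Differentiating these structures in this fashion will facilitate the eligibility requirement for excluding patients with tumors within 2 cm of the proximal bronchial tree".
- **Section 6.2.5.2.8 (Proximal Bronchial Tree Plus 2 cm)** expands the contoured tree by 2 cm and introduces this with the words "As part of adhering to the ineligibility requirements for not enrolling patients with tumors in the zone of the proximal bronchial tree". The rule is: "If the GTV falls within this artificial structure, the patient should not be treated with the protocol therapy". Drawing the expanded structure is optional: "This structure is not required by the protocol, but its construction is suggested to facilitate appropriateness of patient selection". Ruler tools are offered as an alternative.

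On timing, section 4.2 says of the pre-treatment CT that "CT Simulation is acceptable". Section 6.1 allows treatment to start up to 4 weeks after registration.

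**The concern.** One term carries two definitions, and the treatment rule covers a larger volume than the eligibility rule it is meant to implement. Between them lies a band beside the lower trachea where a patient passes the written exclusion criterion but should not receive either regimen on protocol.

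If a site checks location only against 3.2 before registration, it can randomise such a patient and discover the conflict at planning. That leaves a randomised patient who should not be treated. It also leaves unclear whether the enrolment was a deviation: Appendix III, item 4 removes patients entered with significant departures from the criteria, and whether this is one depends on which definition is used.

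Location matters for a toxicity endpoint. Section 1.1.2 cites 2-year freedom from severe toxicity of 83% for peripheral tumors and 54% for central ones in a phase II trial. Those figures are not specific to tumors beside the trachea. They show only why the boundary should be unambiguous.

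**Working it through.** The plan gives no figure to reproduce. The check is a comparison of the texts, followed by a distance calculation to show where the two rules part.

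**Texts side by side**

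| | Section 3.2 | Sections 6.2.5.2.5.2 and 6.2.5.2.8 |
|---|---|---|
| Upper end of the tree | Carina | 2 cm above the carina |
| Other airways | Main, lobar, intermediate, lingular | The same |
| Margin | 2 cm | 2 cm |
| Consequence | Not eligible | Should not be treated on protocol |

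The only substantive difference in content is the distal 2 cm of trachea.

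**Assumed geometry (not from the documents).** The tracheal wall is a straight vertical line. The airways listed in 3.2 begin at carina level, and no bronchus lies nearer than that. Let *h* be the height of the nearest GTV point above the carina and *d* its lateral distance from the tracheal wall, both in cm.

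**Top of the excluded zone along the trachea**

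- Section 3.2: 0 + 2 = 2 cm above the carina.
- Contouring rule: 2 + 2 = 4 cm above the carina.

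**Where the rules disagree**

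- Section 3.2 excludes the point when sqrt(h² + d²) ≤ 2.
- The contouring rule excludes it when d ≤ 2 for h < 2, and when sqrt((h − 2)² + d²) ≤ 2 for h from 2 to 4.
- The gap is therefore d from sqrt(4 − h²) to 2 for h < 2, and d from 0 to sqrt(4 − (h − 2)²) for h from 2 to 4.

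| h (cm) | Lateral range in conflict (cm) |
|---|---|
| 1 | 1.73 to 2.0 |
| 1.5 | 1.32 to 2.0 |
| 2 | 0 to 2.0 |
| 3 | 0 to 1.73 |
| 3.5 | 0 to 1.32 |
| 4 | none |

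At 1 cm above the carina the band is only 2.0 − 1.73 = 0.27 cm wide. The conflict lies mainly 2 to 4 cm above the carina.

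**Example: nearest GTV point 3 cm above the carina and 1 cm lateral**

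- Distance to the carina: sqrt(3² + 1²) = sqrt(10) = 3.16 cm, which is 3.16 − 2 = 1.16 cm outside the 3.2 zone.
- Distance to the top of the contoured tree: sqrt((3 − 2)² + 1²) = sqrt(2) = 1.41 cm, which is 2 − 1.41 = 0.59 cm inside the 6.2.5.2.8 zone.

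**Sensitivity to the assumed airway level.** If a 3.2 airway begins at height *t* instead of 0, the example enters the 3.2 zone when sqrt((3 − t)² + 1) ≤ 2, that is when t ≥ 3 − sqrt(3) = 1.27 cm. The example holds unless the listed airways begin more than about 1.27 cm higher than assumed.

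**The case against.** The strongest reply is that the protocol already shows its intent. Section 6.2.5.2.5 ties the contour to the exclusion, and 6.2.5.2.8 speaks of not enrolling such patients, so the two read naturally as instructions for applying 3.2. That stands as evidence that the wider rule is meant. It does not change 3.2, which carries its own explicit definition, and nothing says that the later section overrides it.

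Second, the check can be made before registration, since CT simulation is accepted as pre-treatment imaging. That is true, but it is not required: note 7 to the study calendar (section 7.0) accepts any one of chest CT, PET or CT simulation. Ruler tools do not help until the user knows whether to measure from the carina or from 2 cm above it.

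Third, few such patients should arise. Entry is limited to peripherally located tumors (section 6.1), and 3.2 lets the PI exclude on other grounds. This stands and is the main reason the point is minor. Section 6.1 gives no distance for peripheral, however, so the word does not settle the boundary.

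Fourth, safety is protected separately. Section 6.2.5.1 caps the airway point dose at 30 Gy in the three-fraction arm and 20.2 Gy in the single-fraction arm. With non-4D simulation, a GTV 1 cm from the trachea leaves the PTV edge 1 − 0.5 = 0.5 cm away, because section 6.2.4.1 adds a 0.5 cm axial margin. The limits would therefore constrain the plan whichever definition is used. That stands on harm, but they act at planning, after a patient may have been randomised.

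Finally, Appendix III, item 4 and section 8.2 provide for removal from study. Removal deals with the consequence after enrolment and does not prevent it.

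**Conclusion.** The concern holds, as a minor internal inconsistency in an operative exclusion criterion. A site applying 3.2 as written can randomise a patient whom 6.2.5.2.8 says should not be treated. Confidence in the mismatch is high because it rests on the wording alone.

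The distances illustrate the size of the gap and depend on the simplified geometry. The documents give no frequency for tumors in this position, so the number of patients affected cannot be estimated, though it is likely to be small. The mismatch is not shown to alter power, the event rate or the treatment comparison.

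**What to change.** In section 3.2, add the distal 2 cm of trachea to the list that defines the proximal bronchial tree. The eligibility criterion then matches 6.2.5.2.5.2 and 6.2.5.2.8, which need no edit. Section 3.2 is the text to correct because the stated purpose of the contour points to the wider rule.

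The cost is one phrase and a slightly narrower eligible population. If enrolment is already complete, state instead which definition was applied when eligibility deviations were reviewed.

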6.2.5.2.6 Whole Lung

Both the right and left lungs should be contoured as one structure. Contouring should be carried out using pulmonary windows. All inflated and collapsed lung should be contoured; however, gross tumor (GTV) and trachea/ipsilateral bronchus as defined above should not be included in this structure.

6.2.5.2.7 PTV Plus 2 cm

As part of the QA requirements for "low dose spillage" listed in 6.2.4.2 above, a maximum dose to any point 2 cm away in any direction is to be determined. To facilitate this QA requirement, an artificial structure 2 cm larger in all directions from the PTV is required. Most treatment planning systems have automatic contouring features that will generate this structure without prohibitive effort at the time of treatment planning.

6.2.5.2.8 Proximal Bronchial Tree Plus 2 cm

As part of adhering to the ineligibility requirements for not enrolling patients with tumors in the zone of the proximal bronchial tree, it is convenient to define an artificial structure 2 cm larger in all directions from the proximal bronchial tree. If the GTV falls within this artificial structure, the patient should not be treated with the protocol therapy. Most treatment

planning systems have automatic contouring features that will generate this structure without prohibitive effort at the time of treatment planning. This structure is not required by the protocol, but its construction is suggested to facilitate appropriateness of patient selection. Alternately, ruler tools in the treatment planning software may be used to ensure protocol compliance.

6.2.6 Documentation Requirements

In general, treatment interruptions should be avoided by preventative medical measures and nutritional, psychological, and emotional counseling. Treatment breaks, including indications, must be clearly documented on the treatment record and communicated to the PI. The total treatment time following the first fraction, must not exceed 10 weeks.

6.2.6.1 Quality of Life Measures

Health related quality of life (HRQOL) will be assessed by study team members using 2 frequently used and validated questionnaires. The European Organisation for Research and Treatment of Cancer Quality of Life Questionnaire [EORTC-QLQ] C30) is a generic HRQOL questionnaire. A lung cancer-specific questionnaire (EORTC QLQ-LC13) will also be used⁴⁰⁻⁴². Patient responses to these questionnaires will be used to analyze and quantify differences, if any, in HRQOL from each SBRT regimen. See Appendix II.

6.2.7 Compliance Criteria

6.2.7.1 Dosimetry Compliance

Section 6 describes appropriate conduct for treatment planning dosimetry. Criteria for both major and minor deviations are provided in the table in Section 6.2.4. In addition to the criteria in section 6.2.4, the table in Section 6.2.5 lists dose volume limits for specific organs and structures. Exceeding these limits by more than 2.5% constitutes a minor protocol violation. Exceeding these limits by more than 5% constitutes a major protocol violation.

6.2.7.2 Treatment Delivery Compliance

Set-up films will be compared to digitally reconstructed radiographs from the same beam's eye view. Deviations of less than 0.5 cm in the transverse plane and 1.0 cm in the craniocaudal plane will be considered compliant. Deviations from 0.5-1.0 cm in the transverse plane and 1.0-1.25 cm in the craniocaudal plane will be considered minor protocol deviations. Deviations greater than those listed as minor will be considered major protocol deviations.

6.2.8 Radiation Toxicity

The most commonly reported side effects from lung SBRT have been pulmonary side effects, likely attributable to radiation induced inflammation (radiation pneumonitis) of surrounding normal lung. The constellation of symptoms associated with radiation pneumonitis includes fatigue, fever, shortness of breath, nonproductive cough, and pulmonary infiltrates on chest x-ray.

Among 37 patients evaluated in a Phase I dose escalation study performed by Timmerman et al., all patients reported fatigue. Six patients reported worsening shortness of breath and non-productive cough and were treated with steroids, inhalers cough medicines, and oxygen therapy. On imaging studies, one patient was noted to have worsening pulmonary infiltration and 25 patients had worsening fibrotic changes. Following SBRT, 10 patients had documented decline of at least 10% predicted in at least one measure of pulmonary function. Other reported toxicities in this Phase I trial included chest wall tenderness and discomfort from the abdominal compression device and one report of grade 3 radiation dermatitis.

An update of this Phase I trial evaluating 47 patients, Grade 2 toxicities reported included pneumonitis, pericardial effusion, pneumonia, and bronchitis. Grade 3 toxicities reported included pneumonitis, hypoxia, dermatitis, pericardial effusion, pneumonitis, and tracheal necrosis.

Timmerman et al later reported the results of a Phase II trial that included 70 patients with a median follow-up of 17.5 months. 58 of 70 patients experienced grade 1-2 toxicity, most commonly fatigue, musculoskeletal discomfort, and radiation pneumonitis. Eight grade 3-4 toxicities were reported including decline in PFT's, pneumonia, pleural effusion, apnea, and skin reaction. Six grade 5 toxicities (deaths) were reported, 4 secondary to bacterial pneumonia, 1 from pericardial effusion, and 1 from massive hemoptysis following local recurrence adjacent to the carina. Further analysis of patients experiencing high grade toxicity revealed that tumor location was a significant predictor. Patients treated for tumors in the peripheral lung had 2-year freedom from severe toxicity of 83% compared with only 54% for patients with central tumors³⁰.

In a retrospective analysis of 138 patients reported by Baumann et al., 60% of patients reported no toxicity. Fourteen patients experienced grade 3-4 toxicity including lung atelectasis, rib fracture, pneumonitis, thoracic pain, pneumonia, decreased lung function, and decreased performance

status. The most commonly reported toxicities included lung fibrosis (n=21), skin rash (n=12), lung atelectasis (n=10), cough (n=9), rib fracture (n=8), thoracic pain (n=6), esophagitis (n=5), and pleural exudates (n=4).

Hara et al reported toxicity outcomes among 59 patients treated for malignant lung tumors with single fraction SBRT ranging from 20-34 Gy. In one patient, grade 2 respiratory symptoms were reported and in one patient with active tuberculosis and interstitial pneumonia, Grade 3 respiratory toxicity requiring oxygen supplementation was reported. Two patients experienced skin erythema.

In another trial of single fraction SBRT, Hof et al reported outcomes among 42 patients treated with a single fraction ranging from 19-30 Gy. Follow up CT scan normal tissue changes (including pneumonitic changes and fibrosis) were noted in the treatment area in 64.3% of patients. However, no CTC grade 3 or 4 toxicities were noted. Minor cough and slightly increased dyspnea were the only clinical toxicities observed.

The Japanese experience was reported retrospectively by Onishi et al. Among 257 patients treated with various dosing schemes (1-22 fractions at 3-12 Gy per fraction). NCI-CTC pulmonary toxicities \geq grade 2 were reported in 10.9% of patients. Grade 3 or 4 toxicities were observed in 5.4% and included bronchitis, esophagitis, dermatitis, and rib fracture. The vast majority of patients experiencing symptomatic pulmonary complications had baseline pulmonary fibrosis or emphysema.

7.0 STUDY CALENDAR

	Pre- Treatment ¹¹	Rx #1 ¹⁰	Rx #2	Rx #3 ⁹	6 wks post- rx	12 wks post- rx	f/u ^{1,11}
H&P ⁸	X	Х	Х	Х	Х	Х	Х
Performance Status	X	X	X	X	X	Х	Х
Evaluation by Thoracic Oncologist	X						
Evaluation by Radiation Oncologist	X						
Pregnancy test	X						
CT C/A/P ⁷	X						
PET-CT scan ⁷	Х						X ²
PFT's ⁶	X						X ³
Tumor Biopsy	X						X4
Blood and urine, collection for DBBR, future analyses ⁵	X						
Toxicity Eval	X	Х	Х	Х	Х	Х	Х
QOL questionnaire	X	X	X	X	X	X	X

¹ At week 6 and 12 post SBRT as noted above, then every 3 months for 1 year, and every 6 months for the next 4 years. Patients will be followed for a total of 5 years.

² PET-CT will be done at 6 months and then as clinically indicated

³ PFTs will be done at 6 months, and annually in follow-up

⁴ Biopsies will be done only if clinically indicated.

⁵Blood and urine will be collected through the DBBR at pre-treatment. Patients may refuse this and still participate in the study. This will not be offered at network sites.

⁶ Full Spirometry and DLCO

⁷ Any one of these pre-treatment imaging studies should be done within 6 weeks of registration: CT Chest, PET or CT Simulation

⁸ H&P within 2 weeks of treatment start

⁹Overall treatment time for one fraction is one day, for three fractions is 8-24 days.

¹⁰Treatment may start within 4 weeks after registration.

¹¹Pre-treament and follow up assessments may be waived at the discretion of the Principal Investigator.

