6.2.1.2 Dose Fractionation

Patients will receive 1 (30 Gy) or 3 (20 Gy) fractions of radiation. A minimum of 40 hours and a maximum of 8 days should separate each treatment. No more than 2 fractions will be delivered per week (7 consecutive days). The dose for all patients per fraction will be to the prescription line at the edge of the PTV. If giving 3 fractions, treatment will be delivered as above over 8-24 days for a total of 60 Gy. Overall treatment time for one fraction is one day, for three fractions is 8-24 days. Treatment may start within 4 weeks after registration.

6.2.1.3 *Premedications*

Unless contraindicated, it is recommended that all patients receive corticosteroid premedication (e.g. Decadron 4 mg p.o. in a single dose, or equivalent) 15-60 minutes prior to each of the treatment for the intended purpose of modulating immediate pulmonary inflammatory effects. Analgesic premedication to avoid general discomfort during long treatment durations also is recommended when appropriate.

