12.0 STATISTICAL ANALYSIS

This is a phase II randomized study to compare incidence of RTOG grade 3 or higher toxicity associated with 2 different, established SBRT regimens for NSCLC.

Group sample sizes of 49 in group one (Gy x 3) and 49 in group two (Gy x 1) achieve 81% power to detect a difference between the group incidences of toxicity of 0.17. The incidence of toxicity in group one (the treatment group) is assumed to be 0.03 under the null hypothesis and 0.2000 under the alternative hypothesis. The proportion in group two (the control group) is 0.03. The test statistic used is the one-sided Z test with continuity correction and unpooled variance. The significance level of the test was targeted at 0.05. The significance level actually achieved by this design is 0.0037.

Descriptive statistics will be presented for each group. Incidence of toxicity will be compared using Z test. Disease free survival and overall survival will be compared between two groups using log-rank test statistics. Correlation analysis will be performed to explore the relationship between outcomes and toxicities with tumor biomarkers. The estimate of acute and long term toxicity associated with SBRT for NSCLC will be reported.

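### Between the first dose and week 6, the calendar schedules two toxicity and QOL assessments in the three-fraction arm and none in the single-fraction arm; the effect on the primary test is probably modest

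*Combined protocol and SAP*

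**What the plan says.** Section 7.0 has one calendar for both arms. The rows "Toxicity Eval" and "QOL questionnaire" are marked before treatment, at Rx #1, Rx #2 and Rx #3, at 6 and 12 weeks after treatment, and in later follow-up. Footnote 1 sets the visits after treatment (the last figure is in years): "At week 6 and 12 post SBRT as noted above, then every 3 months for 1 year, and every 6 months for the next 4". No footnote gives single-fraction patients a substitute for Rx #2 or Rx #3.

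Section 6.2.1.2 fixes the number of treatment visits: "Patients will receive 1 (30 Gy) or 3 (20 Gy) fractions of radiation". On timing it says "Overall treatment time for one fraction is one day, for three fractions is 8-24 days", and on spacing "A minimum of 40 hours and a maximum of 8 days should separate each treatment".

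Three parts of the plan depend on these assessments:

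- Comparing toxicity incidence between the regimens is the primary objective (section 2.1.1).
- QOL is compared as a secondary objective (section 2.2.1). Section 6.2.6.1 adds: "Patient responses to these questionnaires will be used to analyze and quantify differences, if any, in HRQOL from each SBRT regimen".
- Section 12.0 says: "The estimate of acute and long term toxicity associated with SBRT for NSCLC will be reported".

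**The concern.** When two arms are compared on how often an event is recorded, they should be looked at equally often over the same time from randomization or first dose. Here the number of early looks depends on the arm. An acute effect that appears and settles within six weeks of the first dose has two more scheduled chances of being graded in the three-fraction arm.

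The test in section 12.0 is one-sided, and its alternative is more toxicity with three fractions (0.20 against 0.03). The extra looks push towards that conclusion. No blinding and no blinded toxicity review is described, so nothing in the plan offsets the difference.

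Section 1.1.4 makes the point relevant to this trial. It observes that toxicity was followed more closely in earlier multi-fraction studies than in single-fraction ones. Randomization should remove that ambiguity, but the calendar brings part of it back.

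For QOL, early measurements that were never taken cannot be recovered in the analysis.

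**Working it through.** **1. Scheduled assessments (toxicity and QOL alike), counted from the calendar**

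| Interval | 20 Gy x 3 | 30 Gy x 1 |
|---|---|---|
| Day of first dose (Rx #1) | 1 | 1 |
| After that day, before week 6 (Rx #2, Rx #3) | 2 | 0 |
| Week 6 after treatment | 1 | 1 |
| First dose through week 6 | 4 | 2 |
| Last fraction to week 6, exclusive | 0 | 0 |

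This assumes that the Rx #2 and Rx #3 columns do not apply to single-fraction patients and that week 6 is counted from the last fraction. The calendar offers no other reading. The last row shows that the imbalance exists only in time from first dose.

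**2. QOL recall.** The symptom items of both questionnaires in Appendix II ask about the preceding week. In the single-fraction arm, the Rx #1 form describes the week before radiation and the week 6 form covers about days 35 to 42. No form reaches the first five weeks or so. In the three-fraction arm up to two forms do, depending on spacing. If Rx #2 falls at the 40-hour minimum, 168 - 40 = 128 of that form's 168 recall hours precede the first dose.

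**3. Timing of the extra looks.** Two gaps of at most 8 days put the third fraction no later than 2 x 8 = 16 days after the first. The same section allows up to 24 days overall. The week 6 visit falls 42 days after first dose in the single-fraction arm. In the three-fraction arm it falls 16 + 42 = 58 days after first dose at most under the gap limit, or (24 - 1) + 42 = 65 days at most under the overall limit, counted inclusively.

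**4. The plan's own figures.** With 49 per arm, the section 12.0 test rejects when

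Z = (p1 - p2 - c) / sqrt[p1(1 - p1)/49 + p2(1 - p2)/49] >= 1.645, where c = ½(1/49 + 1/49) = 1/49.

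Here p1 and p2 are the observed proportions in the three- and single-fraction arms. Summing the two binomial distributions over all outcomes gives power 0.805 at 0.20 against 0.03 (stated 81%) and a significance level of 0.0037 at 0.03 against 0.03 (stated 0.0037). Both are reproduced.

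**5. Illustration of unequal recording.** Assume both arms have the same true rate p of grade 3 or higher toxicity and that a share m of single-arm events is never recorded. The recorded rates are then p and p(1 - m). The documents do not give m. The 3% is the planning rate in section 12.0, and the 17% is the multi-fraction figure for peripheral tumors in section 1.1.4.

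| True rate p | Share missed m | Recorded rates (three vs single) | Rejection rate |
|---|---|---|---|
| 3% | 0 | 0.03 vs 0.03 | 0.4% |
| 3% | half | 0.03 vs 0.015 | 0.8% |
| 3% | all | 0.03 vs 0 | 1.6% |
| 17% | 0 | 0.17 vs 0.17 | 2.9% |
| 17% | 10% | 0.17 vs 0.153 | 4.6% |
| 17% | 25% | 0.17 vs 0.1275 | 9.2% |

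The third row can be checked directly. With no recorded single-arm events the test needs at least 5 of 49 in the other arm, and P(X >= 5) for a binomial with n = 49 and p = 0.03 is 0.0155.

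**The case against.** Assessing patients when they attend for treatment, and counting follow-up from its completion, is a coherent choice. The extra looks fall on treatment days, no later than the day of the last dose, and from then on both arms are unobserved for the same six weeks. A reader might infer that only the single-fraction arm goes unobserved after its treatment. The calendar does not support that.

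The primary endpoint is also less exposed than the visit counts suggest:

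- Patients are followed for five years, and a phase II trial cited in section 1.1.2 reports a median of 10.5 months to observed toxicity.
- The note on fibrosis in Appendix I places pneumonitis generally within 3 months of radiation, a period that includes weeks 6 and 12.
- The toxicity evaluation, unlike the QOL symptom items, has no one-week recall limit.
- Serious adverse events are reportable whether or not a visit is scheduled, and sections 10.2 and 10.4 cover more than hospitalization.

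All of this stands, and it is why the effect is probably modest. It does not close the gap. Under Appendix I, cough or dyspnea that interferes with daily activities is already grade 3, so it can count as toxicity without being a serious adverse event. Footnote 11 also allows follow-up assessments to be waived.

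On QOL, a reader might infer that an acute comparison has lost one arm entirely. The plan defines no separate acute QOL comparison, and both arms complete weeks 6 and 12. What is missing is early QOL in one arm. The count of two forms against none is a maximum that depends on fraction spacing.

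**Conclusion.** The imbalance is real: two scheduled toxicity and QOL assessments against none between the day of first dose and week 6. It runs in the direction the one-sided test can declare. It mainly affects short-lived acute events and early QOL.

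Its effect on the primary comparison is probably modest, and its size depends on m, which the documents do not give. At the planning rate of 3%, no degree of under-recording in the single-fraction arm takes the rejection rate to the 5% target, since the ceiling is 1.6%. At 17%, missing one event in ten leaves it at 4.6%. Missing one in four takes it to 9.2%.

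A reader might instead add 2 to 4 percentage points to the three-fraction arm at a 3% base, obtain rejection rates of 2.6% (0.05 vs 0.03) to 8.1% (0.07 vs 0.03), and conclude that the test's error rate is seriously inflated at the planning rate. With equal true rates, those inputs mean a true rate of 5% to 7% in both arms, with 2/5 = 40% to 4/7 = 57% of single-arm events never recorded at any visit or by safety reporting. Nothing in the documents supports losses of that size, and such a case is no longer a true rate of 3%.

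**What to change.** **Patients still to be treated.** Amend the calendar so that single-fraction patients have a telephone toxicity evaluation and a mailed or telephone QOL form at two times from first dose matching Rx #2 and Rx #3. Before setting those times, reconcile the 8-day maximum gap in section 6.2.1.2 with the 8-24 day overall time in the same section, because together they determine when Rx #2 and Rx #3 can fall.

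**Patients already treated.** Add a sensitivity analysis of the primary comparison that counts only events recorded at assessments common to both arms: Rx #1, week 6, week 12 and later. An event first seen at Rx #2 or Rx #3 and still recorded at week 6 would count. List separately the events recorded only at Rx #2 or Rx #3. For QOL, state that no early single-fraction data exist for these patients and base the between-arm comparison on the common times.

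**Cost.** At most 49 x 2 = 98 short contacts by existing staff, fewer if some single-fraction patients have already passed those times, plus one extra tabulation. Sample size and treatment are unchanged.
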